7.1 Adverse events

An adverse event (AE) is any untoward medical occurrence (e.g., any unfavorable and unintended sign, including abnormal laboratory findings, symptom or disease) in a clinical investigation subject *after providing informed consent* for participation in the study until the end of study visit. Therefore, an AE may or may not be temporally or causally associated with the use of a medicinal (investigational) product.

In addition, all reports of intentional misuse and abuse of the product are also considered an adverse event irrespective if a clinical event has occurred.

The occurrence of AEs must be sought by non-directive questioning of the subject at each visit during the study. Adverse events also may be detected when they are volunteered by the subject during or between visits or through physical examination, laboratory test, or other assessments.

Abnormal laboratory values or test results constitute AEs only if they fulfill at least one of the following criteria:

- they induce clinical signs or symptoms,
- they are considered clinically significant,
- they require therapy.

Clinically significant abnormal laboratory values or test results must be identified through a review of values outside of normal ranges/clinically notable ranges, significant changes from baseline or the previous visit, or values which are considered to be non-typical in a patient with underlying disease. Investigators have the responsibility for managing the safety of individual subject and identifying AEs. Alert ranges for laboratory and other test abnormalities are included in Appendix 7.

Adverse events must be recorded in the Adverse Events CRF under the signs, symptoms or diagnosis associated with them, accompanied by the following information:

- the severity grade
 - mild: usually transient in nature and generally not interfering with normal activities
 - moderate: sufficiently discomforting to interfere with normal activities
 - severe: prevents normal activities
- Its relationship to the study treatment and other investigational treatment
 - "No Relationship to study treatment or other investigational treatment" or
 - "Relationship to study treatment" or
 - "Relationship to other investigational treatment" or
 - "Relationship to both study treatment and other investigational treatment or indistinguishable"
- its duration (start and end dates) or if the event is ongoing an outcome of not recovered/not resolved must be reported
- whether it constitutes a serious adverse event (SAE See Section 7.2 for definition of SAE) and which seriousness criteria have been met
- action taken regarding investigational treatment.

The action taken to treat the AE should be recorded on the Adverse Event eCRF.

All adverse events must be treated appropriately. Treatment may include one or more of the following:

- no action taken (e.g. further observation only)
- investigational treatment dosage increased/reduced •
- investigational treatment interrupted/withdrawn
- concomitant medication or non-drug therapy given
- patient hospitalized/patient's hospitalization prolonged (see Section 7.2 for definition of SAE)
- its outcome (not recovered/not resolved; recovered/resolved; recovering/resolving, recovered/resolved with sequelae; fatal; or unknown)

Once an AE is detected, it must be followed until its resolution or until it is judged to be permanent, and assessment must be made at each visit (or more frequently, if necessary) of any changes in severity, the suspected relationship to the study drug, the interventions required to treat it, and the outcome.

The investigator must also instruct each subject to report any new AE (beyond the protocol observation period) that the subject, or the subject's personal physician, believes might reasonably be related to study treatment. This information must be recorded in the investigator's source documents; however, if the AE meets the criteria of an SAE, it must be reported to Novartis

7.2 Serious adverse events

7.2.1 **Definition of SAE**

An SAE is defined as any AE [appearance of (or worsening of any pre-existing)] undesirable sign(s), symptom(s) or medical conditions(s)) which meets any one of the following criteria:

- is fatal or life-threatening
- results in persistent or significant disability/incapacity
- constitutes a congenital anomaly/birth defect
- requires inpatient hospitalization or prolongation of existing hospitalization, unless hospitalization is for:
 - routine treatment or monitoring of the studied indication, not associated with any deterioration in condition (specify what this includes)
 - elective or pre-planned treatment for a pre-existing condition that is unrelated to the indication under study and has not worsened since signing the informed consent
 - treatment on an emergency outpatient basis for an event not fulfilling any of the definitions of a SAE given above and not resulting in hospital admission
 - social reasons and respite care in the absence of any deterioration in the patient's general condition
- is medically significant, e.g. defined as an event that jeopardizes the patient or may require medical or surgical intervention.

All malignant neoplasms will be assessed as serious under "medically significant" if other seriousness criteria are not met.

Life-threatening in the context of a SAE refers to a reaction in which the patient was at risk of death at the time of the reaction; it does not refer to a reaction that hypothetically might have caused death if it were more severe (please refer to Annex IV, ICH-E2D Guideline).

Medical and scientific judgment should be exercised in deciding whether other situations should be considered serious reactions, such as important medical events that might not be immediately life threatening or result in death or hospitalization but might jeopardize the subject or might require intervention to prevent one of the other outcomes listed above. Examples of such events are intensive treatment in an emergency room or at home for allergic bronchospasm, blood dyscrasias or convulsions that do not result in hospitalization or development of dependency or abuse (please refer to Annex IV, ICH-E2D Guideline).

Any suspected transmission via a medicinal product of an infectious agent is also considered a serious adverse reaction.

All AEs (serious and non-serious) are captured on the CRF; SAEs also require individual reporting to Drug Safety and Epidemiology as per Section 7.2.2.

7.2.2 SAE reporting

To ensure patient safety, every SAE, regardless of causality, occurring after the patient has provided informed consent and until 10 weeks (70days) after the last study visit, or 12 Weeks (84 days) following the last administration of study treatment, or 30 days after the subject has stopped study participation (whichever is later) must be reported to Novartis within 24 hours of learning of its occurrence.

Any SAEs experienced after this period should only be reported to Novartis if the investigator suspects a causal relationship to study treatment.

All follow-up information for the SAE including information on complications, progression of the initial SAE and recurrent episodes must be reported as follow-up to the original episode within 24 hours of the investigator receiving the follow-up information. An SAE occurring at a different time interval or otherwise considered completely unrelated to a previously reported one must be reported separately as a new event.

Information about all SAEs is collected and recorded on the Serious Adverse Event Report Form; all applicable sections of the form must be completed in order to provide a clinically thorough report. The investigator must assess the relationship of each SAE to each specific component of study treatment, (if study treatment consists of several components) complete the SAE Report Form in English, and submit the completed form within 24 hours to Novartis. Detailed instructions regarding the submission process and requirements for signature are to be found in the investigator folder provided to each site.

Follow-up information is submitted as instructed in the investigator folder. Each re-occurrence, complication or progression of the original event must be reported as a follow-up to that event regardless of when it occurs. The follow-up information should describe whether the event has resolved or continues, if and how it was treated, whether the blind was broken or not, and whether the patient continued or withdrew from study participation.

If the SAE is not previously documented in the Investigator's Brochure or Package Insert (new occurrence) and is thought to be related to the study treatment a Drug Safety and Epidemiology Department associate may urgently require further information from the investigator for health authority reporting. Novartis may need to issue an Investigator Notification (IN) to inform all investigators involved in any study with the same study treatment that this SAE has been reported. Suspected Unexpected Serious Adverse Reactions (SUSARs) will be collected and reported to the competent authorities and relevant ethics committees in accordance with EU Guidance 2011/C 172/01 or as per national regulatory requirements in participating countries.

7.3 Liver safety monitoring

To ensure patient safety and enhance reliability in determining the hepatotoxic potential of an investigational drug, a standardized process for identification, monitoring and evaluation of liver events has to be followed.

The following two categories of abnormalities / adverse events have to be considered during the course of the study (irrespective of whether classified/reported as (S)AE):

- Liver laboratory triggers, which will require repeated assessments of the abnormal laboratory parameter
- Liver events, which will require close observation, follow-up monitoring and completion of the standard base liver CRF

Please refer to Table 18-1 in Appendix 6 for complete definitions of liver laboratory triggers and liver events.

Every liver laboratory trigger or liver event as defined in Table 18-1 in Appendix 6 should be followed up by the investigator or designated personal at the trial site as summarized below.

Detailed information is outlined in Table 18-2 in Appendix 6.

For the liver laboratory trigger:

• Repeating the liver function test (LFT) within the next week to confirm elevation or resolution.

These LFT repeats should be performed using the central laboratory if possible. If this is not possible, then the repeats can be performed at a local laboratory to monitor the safety of the subject. Repeats laboratory must then be performed at central laboratory as soon as possible. If a liver event is subsequently reported, any local LFTs previously conducted that are associated with this event should be reported on the Liver CRF. If the elevation is confirmed, close observation of the patient will be initiated, including consideration of treatment interruption if deemed appropriate.

For the liver events:

- Repeating the LFT to confirm elevation as appropriate
- Discontinuation of the investigational drug if appropriate
- Hospitalization of the patient if appropriate
- A causality assessment of the liver event via exclusion of alternative causes (e.g. disease, co-medications)
- An investigation of the liver event which needs to be followed until resolution.

These investigations can include serology tests, imaging and pathology assessments, hepatologist's consultancy, based on investigator's discretion. All follow-up information, and the procedures performed must be recorded on the appropriate CRF, including the liver event overview CRF.

7.4 Renal safety monitoring

To date, there has been no safety signal for nephrotoxicity with secukinumab in over 12,000 patients and healthy subjects exposed, and from a mechanism of action standpoint there is no known effect of blocking IL-17A on the kidney. All subjects with laboratory tests resulting in clinically significant abnormal values (see Appendix 7 for notable laboratory values) are to be followed until the values return to normal ranges or until a valid reason, other than treatment related AE, is defined. Standard renal function tests (blood urea nitrogen, serum creatinine) will be obtained at regular intervals, but special measures for renal safety monitoring are not planned.

7.5 Reporting of study treatment errors including misuse/abuse

Medication errors are unintentional errors in the prescribing, dispensing, administration or monitoring of a medicine while under the control of a healthcare professional, patient or consumer (EMA definition).

Misuse refers to situations where the medicinal product is intentionally and inappropriately used not in accordance with the protocol.

Abuse corresponds to the persistent or sporadic, intentional excessive use of a medicinal product, which is accompanied by harmful physical or psychological effects.

Study treatment errors and uses outside of what is foreseen in the protocol will be collected in the DAR (dose administration record) eCRF irrespective of whether or not associated with an AE/SAE and reported to Safety only if associated with an SAE. Misuse or abuse will be collected and reported in the safety database irrespective of it being associated with an AE/SAE.

Table 7-1 Study treatment

Treatment error type	Document in Dose Administration (DAR) eCRF (Yes/No)	Document in AE eCRF	Complete SAE form
Unintentional study treatment error	Yes	Only if associated with an AE	Only if associated with an SAE
Misuse/Abuse	Yes	Yes,	Yes, even if not associated with a SAE

7.6 Pregnancy reporting

To ensure subject safety, each pregnancy occurring while the patient is on study treatment must be reported to Novartis/Contract Research Organization (CRO) within 24 hours of learning of its occurrence. The pregnancy should be followed up to determine outcome, including spontaneous or voluntary termination, details of the birth, and the presence or absence of any birth defects, congenital abnormalities, or maternal and/or newborn complications.

Pregnancy must be recorded on the Pharmacovigilance Pregnancy Form and reported by the investigator to the local Novartis Drug Safety and Epidemiology Department. Pregnancy follow-up should be recorded on the same form and should include an assessment of the possible relationship to the study treatment.

Any SAE experienced during the pregnancy and unrelated to the pregnancy must be reported on a SAE form.

8 Data review and database management

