3.1 Study design

This is a randomized, double-blind, active control, multicenter, parallel-group trial evaluating secukinumab monotherapy and adalimumab monotherapy in approximately 850 subjects with active PsA. A screening period of up to 8 weeks before randomization will assess subject eligibility (see Figure 3-1). Efficacy assessments will occur through Study Week 52. Two follow-up visits at Week 60 and 68 will occur thereafter. Total maximum study duration, including screening period, is up to 76 weeks.

At Baseline (BSL), subjects whose eligibility is confirmed will be randomized to one of two groups (1:1): Group 1 (secukinumab 300 mg) with approximately 425 subjects or Group 2 (adalimumab 40 mg) with approximately 425 subjects. In order to maintain the blind, both groups will receive 1 or 2 placebo s.c. injections to keep consistency in the number of injections at each dosing visit. Secukinumab (300 mg) is available in 2 x 1.0 mL pre-filled syringes (PFS) and adalimumab is available in 1 x 0.4 mL PFS. Placebo (1.0 and 0.5 mL PFS) is also available.

Group 1 - Secukinumab 300 mg s.c.

Secukinumab 300 mg (2 x 1 mL PFS) will be administered at Baseline, Weeks 1, 2, 3 and 4, followed by dosing every 4 weeks until Week 48.

In addition, all Group 1 subjects will receive placebo (1 x 1mL PFS) at given visits in order to maintain the blind (see Figure 3-1; Table 5-1).

Group 2 - Adalimumab 40 mg s.c.

Adalimumab 40 mg (1 x 0.4mL PFS) will be administered at Baseline followed by dosing every 2 weeks until Week 50.

[figure not shown]
In addition, all Group 2 subjects will receive placebo (1 x 0.5mL or 2 x 0.5mL PFS) at given visits in order to maintain the blind (see Figure 3-1; Table 5-1).

Study staff involved in drug handling and administration (e.g., investigational treatment receipt, inventory, storage, administration, and accountability) and IRT processes, will be unblinded and must not be the investigator or study staff involved in safety and efficacy assessments or eCRF completion. In addition, investigational treatment administered by the designated study staff member who is unblinded to treatment assignment must be done in a manner that maintains subject blinding as described in the Study Reference Manual. All other subject-related activities will be managed by blinded site personnel throughout the study.

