4.2 Exclusion criteria

Patients fulfilling any of the following criteria are not eligible for inclusion in this study. No additional exclusions may be applied by the investigator, in order to ensure that the study population will be representative of all eligible subjects.

- 1. Pregnant or nursing (lactating) women, where pregnancy is defined as the state of a female after conception and until the termination of gestation, confirmed by a positive human chorionic gonadotropin (hCG) laboratory test.
- 2. Women of childbearing potential, defined as all women physiologically capable of becoming pregnant, unless they are using effective methods of contraception during dosing of study treatment and minimum 16 weeks or longer if local label requires it after the last dose (e.g. 20 weeks for secukinumab, 5 months for adalimumab in EU). Effective contraception methods include:
 - Total abstinence (when this is in line with the preferred and usual lifestyle of the subject. Periodic abstinence (e.g., calendar, ovulation, symptothermal, post-ovulation methods) and withdrawal are not acceptable methods of contraception.
 - Female sterilization (have had surgical bilateral oophorectomy with or without hysterectomy), total hysterectomy or tubal ligation at least six weeks before taking investigational drug. In case of oophorectomy alone, only when the reproductive status of the woman has been confirmed by follow up hormone level assessment.
 - Male sterilization (at least 6 months prior to screening). For female subjects on the study, the vasectomized male partner should be the sole partner for that subject.
 - Barrier methods of contraception: Condom or Occlusive cap (diaphragm or cervical/vault caps). For UK: with spermicidal foam/gel/film/cream/vaginal suppository.
 - Use of oral, (estrogen and progesterone), injected or implanted hormonal methods of contraception or other forms of hormonal contraception that have comparable efficacy (failure rate <1%), for example hormone vaginal ring or transdermal hormone contraception or placement of an intrauterine device (IUD) or intrauterine system (IUS). In case of use of oral contraception, women should have been stable on the same pill for a minimum of 3 months before taking investigational drug.

In case local regulations deviate from the methods listed, local regulations apply and will be described in the ICF.

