10.2 Informed consent procedures

Eligible subjects may only be included in the study after providing IRB/IEC-approved informed consent (witnessed, where required by law or regulation), or, if incapable of doing so, after such consent has been provided by a legally acceptable representative(s) of the subject. In cases where the subject's representative gives consent, the subject should be informed about the study to the extent possible given his/her understanding. If the subject is capable of doing so, he/she must indicate assent by personally signing and dating the informed consent document or a separate assent form. Informed consent must be obtained before conducting any study-specific procedures (e.g. all of the procedures described in the protocol). The process of obtaining informed consent must be documented in the patient source documents.

Novartis will provide to investigators in a separate document a proposed informed consent form that complies with the ICH GCP guideline and regulatory requirements and is considered appropriate for this study. Any changes to the proposed consent form suggested by the investigator must be agreed to by Novartis before submission to the IRB/IEC, and a copy of the approved version must be provided to the Novartis monitor after IRB/IEC approval.

Women of child bearing potential must be informed that taking the study treatment may involve unknown risks to the fetus if pregnancy were to occur during the study and agree that in order to participate in the study they must adhere to the contraception requirement for the duration of the study, and for a minimum 16 weeks or longer if local label requires it (e.g. 20 weeks for secukinumab, 5 months for adalimumab in EU) after the last dose. If there is any question that the subject will not reliably comply, they should not be entered in the study.

The study includes an optional PG ICF which requires a separate signature if the subject agrees to participate. It is required as part of this protocol that the Investigator presents this option to the subject. The process for obtaining consent should be exactly the same as described above for the main informed consent.

Declining to participate in these PG assessments will in no way affect the patient's ability to participate in the main research study.

In the event that Novartis wants to perform testing on the samples that are not described in this protocol, additional IRB and/or IEC approval will be obtained.

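### Section 7.6 requires pregnancy reporting only while a woman is on study treatment and does not expressly cover conceptions in the post-dose contraception period of Sections 4.2 and 10.2

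*Protocol*

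**What the plan says.** **Reporting duty.** Protocol Section 7.6 states that "each pregnancy occurring while the patient is on study treatment must be reported" to the sponsor or CRO within 24 hours of the site learning of it. Such a pregnancy is then followed to its outcome, including termination, birth details and any abnormality. A second paragraph names the form to use. The section gives no period after the last dose.

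**Contraception duty.** Exclusion criterion 2 in Section 4.2 requires effective contraception during dosing and for a "minimum 16 weeks or longer if local label requires it after the last dose", with the examples "e.g. 20 weeks for secukinumab, 5 months for adalimumab in EU". Section 10.2 repeats these periods for the consent discussion and adds that "they must adhere to the contraception requirement for the duration of the study". Its stated reason is that "taking the study treatment may involve unknown risks to the fetus if pregnancy were to occur during the study".

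**Dosing and follow-up.** Under Section 3.1, secukinumab is given at Baseline and Weeks 1 to 4, "followed by dosing every 4 weeks until Week 48". Adalimumab is given at Baseline, "followed by dosing every 2 weeks until Week 50". "Two follow-up visits at Week 60 and 68 will occur thereafter", that is, after the Week 52 assessments. Section 6 gives women who leave the study early two follow-up visits, 12 and 18 weeks after their last study treatment.

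**The concern.** The contraception rule and the consent text treat the weeks after the last dose as a period in which a pregnancy could still matter for the fetus. The reporting rule, read as written, stops with treatment. A site that follows Section 7.6 to the letter need not notify the sponsor of a pregnancy conceived in those weeks, and nobody is required to establish how it ended.

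The same applies to women who stop treatment early and stay in the study. Section 5.5.9 keeps them in the study and lets them attend later visits, so they can be under observation and inside the contraception period but outside the reporting window.

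What is at stake is safety information. Pregnancies with drug exposure may be few, so each omitted case could matter to the record for either drug. Amendment 01 updated both the follow-up schedule and the contraception wording in line with the adalimumab label, and the current Section 7.6 has no matching period.

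**Working it through.** The plan states no figure for this point, so the check sets the time windows side by side.

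**Inputs**
- Last active dose: Week 48 for secukinumab, Week 50 for adalimumab (Section 3.1). Injections at site run through Week 50 (Section 5.1.1).
- Contraception after the last dose: at least 16 weeks; examples 20 weeks and 5 months (Section 4.2).
- Last follow-up visit: Week 68 (Section 3.1).
- On-treatment limit used for other data: last dose + 84 days, or 12 weeks (SAP 2.9.2 and 2.9.3, laboratory data and vital signs).
- Assumption: 5 months = 5 × 365.25 / 12 / 7 = 21.7 weeks.

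**Formulas**
- End of contraception period = last-dose week + contraception weeks.
- Uncovered weeks = end of contraception period − end of the Section 7.6 window.

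Three readings of where that window ends are shown: (a) the last dose; (b) Week 52, the end of the final dosing interval (48 + 4 or 50 + 2); (c) last dose + 12 weeks.

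| Case | Contraception ends | Uncovered (a) | Uncovered (b) | Uncovered (c) |
|---|---|---|---|---|
| Secukinumab, 16 weeks | 48 + 16 = Week 64 | 16 | 64 − 52 = 12 | 16 − 12 = 4 |
| Secukinumab, 20 weeks | 48 + 20 = Week 68 | 20 | 68 − 52 = 16 | 20 − 12 = 8 |
| Adalimumab, 16 weeks | 50 + 16 = Week 66 | 16 | 66 − 52 = 14 | 16 − 12 = 4 |
| Adalimumab, 5 months | 50 + 21.7 = Week 71.7 | 21.7 | 71.7 − 52 = 19.7 | 21.7 − 12 = 9.7 |

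The gap is positive in every cell.

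**Comparison with SAE reporting (Section 7.2.2).** That window ends at the latest of three dates. For a woman who completes the study these are:
- 10 weeks after the last visit: 68 + 10 = Week 78.
- 12 weeks after the last dose: at most 50 + 12 = Week 62.
- 30 days after participation stops: 68 + 30/7 = Week 72.3.

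The latest is Week 78, which is past the longest contraception example (Week 71.7). Pregnancy reporting, as written, ends earlier than either.

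**Other text that might close the gap.** No other section extends pregnancy reporting past the last dose. Section 7.2.1 makes a congenital anomaly or birth defect an SAE. Section 7.6 sends an SAE that occurs during a pregnancy and is unrelated to it to the SAE form. Neither makes the pregnancy itself reportable.

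**The case against.** **Serious outcomes are already covered.** In part. A birth defect, or another outcome meeting an SAE criterion, is reportable under Section 7.2.2 to about Week 78 for completers, and later if the investigator suspects a causal link. An uncomplicated pregnancy meets no SAE criterion. Without notice of the pregnancy nobody is required to follow it, and a conception in the post-dose period could lead to a birth well after Week 78, when only suspected causality triggers a report.

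**The phrase is undefined.** This stands as a qualification. Section 7.6 does not say when a woman ceases to be on study treatment, and its second paragraph carries no time limit of its own. The 84-day limit in the SAP governs laboratory and vital-sign summaries, not pregnancy reports, and would still leave about 4 to 10 weeks uncovered. The second paragraph reads as an instruction on how to record pregnancies already in scope.

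**Exposed pregnancies found at Week 60 or 68 are lost.** A reader might infer this stronger point, but the documents do not support it. Section 7.6 depends on when the pregnancy occurs, and its 24-hour clock starts when the site learns of it. A pregnancy conceived on treatment and discovered at a follow-up visit remains reportable. Only conceptions after treatment ends are affected.

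**The numbers will be small.** Probably so. The documents give neither the number of women of childbearing potential nor an expected number of pregnancies. This limits the priority of the point but does not remove the mismatch.

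**Conclusion.** The point holds in a limited form. Section 7.6 does not expressly require reporting or outcome follow-up for a pregnancy conceived after the last dose but within the contraception period of Sections 4.2 and 10.2. The three sections should be reconciled.

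On the plain reading the uncovered time is at least 16 weeks per woman, 20 weeks in the secukinumab example and about 21.7 weeks in the adalimumab EU example. On the most generous reading found in the documents it is 4, 8 and about 9.7 weeks. These figures assume the last-dose weeks in Section 3.1 and 5 months of average length. A longer local label would widen the gap.

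Two stronger conclusions should not be drawn. First, post-dose pregnancies are not barred from being reported: Section 7.6 simply does not require it, and serious outcomes retain the SAE route. Second, the share of study weeks falling after the last injection does not measure impact. It is calendar time, applies only to women of childbearing potential, and takes no account of the chance of conception or of residual drug exposure.

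This is a cheap improvement to safety capture. It has no bearing on the estimand, the hypothesis tests, power or type I error.

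**What to change.** Extend the Section 7.6 window past the last dose and tie it to Sections 4.2 and 10.2. The end-point should be the same in both arms. The label examples differ by drug and investigators are blinded (Section 5.4), so an arm-specific end date could not be applied without revealing treatment.

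Two common end-points would work:

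- **The last follow-up visit:** Week 68, or the 18-week follow-up visit for women who leave the study early. This is the simplest to run. Week 68 is 68 − 50 = 18 weeks after the last injection visit, so it covers the 16-week minimum in both arms. It stops about 71.7 − 68 = 3.7 weeks short of the 5-month example.
- **The longest contraception period applicable under the protocol, counted from the last injection in either arm.** With the 5-month example this ends at about Week 71.7 for completers. It covers every stated period, but the final weeks fall after the last visit and would need a telephone contact or an instruction to the woman to report. The SAE window already runs past that date.

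Possible wording for the second option: *every pregnancy that begins between the first injection and the end of the longest contraception period applicable in the study, counted from the last injection and identical for both arms, is reported within 24 hours of the site becoming aware of it and followed to outcome.*

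The cost is one sentence, a few more pregnancy forms and follow-ups, and a written amendment with the approvals that Section 11.1 requires. No analysis changes.
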